#### 6.2. Secondary outcome variable(s)

The relative hazard of the any re-operation of the index joint and mortality within 1 year in the intervention compared to the control group will be assessed by fitting adjusted Cox proportional hazards models (see "*Statistical methods*"), and a risk increase of >20% within one year will be considered clinically relevant.

#### Any re-operation

Re-operation will be treated as a binary categorical variable, recorded together with an underlying time-to-event variable, and will be defined as the occurrence of any surgical procedure performed on the previously treated hip within one year after surgery. The occurrence of re-operations is assessed by linking study participants with the NPR as described above, and will be defined by registration of at least one of the specified ICD or NOMESCO codes (Appendix 1).

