#### 4.2. Exclusion criteria

- · Previous inclusion of contralateral hip in the present study
- Pathological or stress fracture of the femoral neck, or fracture adjacent to a previous ipsilateral hip implant
- Unavailability of both interventions for a study participant (e.g., sensitivity to any of the components in the bone cement)
- Patients that have actively marked their hospital charts with an added privacy notice

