#### 4.3. Subject enrolment and randomization

In the first step of the study, the orthopedic departments included are randomized to start with either the control or intervention treatment. After the first period of 2 years is completed, the study site will change to use the other treatment for the patients included in the following period of 2 years. At each department, information regarding the study is made available on the official web page, the orthopedic ward and the outpatient department. All patients admitted and fulfilling the inclusion criteria and registered in the SFR or SAR will be included. After the index surgery, procedural details and patient characteristics will be collected within the SAR. Procedural details include type and brand of implant, type of components (uni- or bipolar head), type of cement (intervention: DIAC or control: Single-impregnated antibiotic-laden bone cement), surgical approach and type of antibiotic prophylaxis. Patient characteristics registered in the SAR include indication for surgery, age, sex, American Society of Anesthesiologists (ASA) grade and body mass index (BMI). Data on revision surgery performed and on reoperations are registered in the SAR. Data on reoperations are also registered in the NPR. Mortality data are automatically available within the SFR and SAR from the SDR.

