## 6. STUDY MEASUREMENTS AND VARIABLES

#### 6.1. Primary outcome variable

Periprosthetic joint infection of the index joint within one year

The definition of PJI will be that the treating physicians defined presence of a PJI and started treatment (re-operation, or suppressive antibiotics, or combinations thereof). The investigators will use the SFR, NPR, SAR and the SDR to identify potential PJI by the registration of any of the International Classification of Diseases (ICD; version 10) codes or NOMESCO codes indicative of

	DAICY	
Clinical Study Protocol	Version No:	1.0
	Date:	2021-11-17

this complication (see Appendix 1). In cases when these codes are present a review of the medical records will be performed to identify patients.

The hazard of infection in the intervention compared to the control group will be assessed by fitting adjusted Cox proportional hazards models.

The review of medical records will capture any re-operation records for surgery related to the index hip fracture, details of antibiotics prescribed, microbiology reports if samples of the suspected infected tissues around the hip were sent for analysis.

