## 7.3. Data storage and management

All data are recorded, handled and stored in a way that allows its accurate reporting, interpretation and verification. All source data at each participating study center, a copy of the completed study database, original protocol with amendments and the final report will be stored at the Orthopedic Department at Umeå University Hospital for a minimum period of 15 years after termination of the trial.

At the conclusion of the study, the occurrence of any protocol deviations will be determined. Data from the SFR on all study participants will be fused with all data on the aforementioned study participants available in the SAR and the SDR one year after the inclusion of the last patient. This combined dataset will then be sent to the NPR to obtain all registered ICD and NOMESCO codes for all study participants from the date of inclusion and onward. After these actions have been completed and the database has been declared to be complete and accurate, it will be locked and available for data analysis.

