# Appendix 1. ICD codes for primary and secondary outcomes.

Endpoint	ICD	NOMESCO
Periprosthetic joint infection	M00.0, M00.0F, M00.1, M00.2, M00.2F, M00.8, M00.8F, M00.9, M00.9F, M86.0F, M86.1F, M86.6, M86.6F, T81.4, T84.5, T84.5F, T84.5X, T84.7, T84.7F	NFSx, NFA12, TNF05, TNF10
Any reoperation		Any of the codes above, and: NFA00-22, NFA31-32, NFCx, NFF01-12, NFL09- 19, NFL39-49, NFL69-99, NFM09-29, NFM49, NFM79-99, NFTx, NFWx
Endpoint	ATC	Minimum number of tablets
Drug prescription	J01XX08: 56 st J01XA02: 28 st J01XA01: 56 st J04AB02: 28 st J01XC01: 168 st J01XC01: 168 st J01CF05: 84 st J01FF01: 56 st J01CA04: 84 st P01AB01: 84 st J01AB01: 84 st J01MA02: 56 st J01MA12: 28 st J01MA14: 28 st J01DE02: 168 st J01DB05: 56 st J01DD04: 28 st J01DD04: 28 st J01FA06: 56 st J01FA15: 56 st J01FA15: 56 st J01FA15: 56 st	56 st 28 st 56 st 28 st 28 st 168 st 84 st 56 st 5

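### Section 6.2 limits re-operation to the treated hip, but its case rule is any listed code in the patient register with no side restriction, so procedures on the other hip can be counted

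*Protocol*

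**What the plan says.** Section 6.2 of the protocol gives a concept and a case rule for re-operation.

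- **Concept:** "any surgical procedure performed on the previously treated hip within one year after surgery". The opening of Section 6.2 likewise speaks of the index joint, plans an adjusted Cox model, and calls a risk increase above 20% within one year clinically relevant.
- **Source:** "The occurrence of re-operations is assessed by linking study participants with the NPR as described above".
- **Case rule:** the outcome "will be defined by registration of at least one of the specified ICD or NOMESCO codes (Appendix 1".

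The re-operation row of Appendix 1 reads "Any of the codes above, and: NFA00-22, NFA31-32, NFCx" and goes on to further procedure groups. No entry is marked left or right. Section 7.3 says the NPR will be used to "obtain all registered ICD and NOMESCO codes for all study participants from the date of inclusion and onward" and mentions no item for side.

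Other sections bear on how a case is confirmed:

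- Section 6.1, on PJI, uses codes only to flag potential cases: "In cases when these codes are present a review of the medical records will be performed to identify patients".
- Section 4.3: "Data on revision surgery performed and on reoperations are registered in the SAR" (SAR is the Swedish Arthroplasty Register).
- The data-collection table in Section 7.2 marks the Swedish Fracture Register (SFR), the hip arthroplasty register, the NPR and medical charts as sources for re-operation.
- Section 7.1 assumes adequate data quality with confirmation in individual charts. It analyses secondary event outcomes like the primary one, as a risk difference from linear regression on cluster-period proportions, and adds odds ratios as a supplementary analysis.

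**The concern.** The concept and the case rule do not select the same events. A patient who has a listed procedure on the other hip within the year meets the rule but not the concept. For PJI, a chart review stands between code and case. For the codes that only the re-operation row adds, no such step is stated.

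Such events would be expected at the same rate under both cements, because they say nothing about the cement in the index hip. Equal false positives in both arms raise the event rate and pull ratio measures towards 1. That matters for the Cox hazard ratio, for the odds ratio, and for the comparison with the protocol's own relative threshold of more than 20%. It works against seeing benefit and against seeing harm.

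**Working it through.** **1. Does the text restrict the side anywhere?**

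| Place | What it contributes | Side restriction? |
|---|---|---|
| 6.2, concept | index hip | yes, as an intention |
| 6.2, case rule | one listed code via the NPR | no |
| Appendix 1 | code list | no |
| 7.3 | request for all codes after inclusion | no |
| 6.1, chart review | would show surgery on the index hip | only for patients with a PJI code |
| 7.2, table | lists SFR, arthroplasty register, NPR and charts | source list only, no rule |
| 4.2 | excludes "Previous inclusion of contralateral hip in the present study" | bars a second enrolment; removes no later other-hip code |

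The restriction exists as an intention. It is missing from the rule that decides a case.

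**2. The plan's own figures.** The protocol states no event rate or power for re-operation, so there is no figure of its own to reproduce for this outcome. Its figures for PJI do reproduce. The 15 yearly volumes sum to 1,747, and 4 × 1,747 = 6,988, against the stated 7,000. Simulating the stated logit model (4,000 data sets, unweighted cluster-period regression without the proportion-female covariate, larger correlation read as within-period) gives power of 89.6%, 87.3% and 80.2%, against the stated 90%, 86% and 80%. Nothing below changes those figures.

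**3. Effect of equal other-hip events (illustration).** The inputs are assumptions, not document figures: control risk p0 = 5%, and other-hip risk f = 0.5% to 3%, equal in both arms and independent of the index hip.

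- Observed risk: q = 1 − (1 − p)(1 − f).
- Observed risk difference: q1 − q0 = (1 − f)(p1 − p0).
- Observed hazard ratio: ln(1 − q1) / ln(1 − q0).

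Example with a true risk ratio of 1.20 (p1 = 6%) and f = 1%: q0 = 1 − 0.95 × 0.99 = 0.0595 and q1 = 1 − 0.94 × 0.99 = 0.0694. The difference is 0.0099, against a true 0.0100. The hazard ratio is 1.173, against a true 1.206. The odds ratio is (0.0694/0.9306)/(0.0595/0.9405) = 1.179, against a true (0.06/0.94)/(0.05/0.95) = 1.213.

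| f | Risk difference retained | HR, true 1.206 | HR, true 0.745 (risk ratio 0.75) | Power, true risk ratio 0.75 |
|---|---|---|---|---|
| 0 | 100% | 1.206 | 0.745 | 72% |
| 0.5% | 99.5% | 1.188 | 0.768 | 68% |
| 1% | 99% | 1.173 | 0.787 | 63% |
| 2% | 98% | 1.148 | 0.817 | 56% |
| 3% | 97% | 1.129 | 0.840 | 50% |

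Power is for two proportions with 6,988 / 2 = 3,494 per arm and ignores clustering. It shows the direction and rough size of the loss, not the trial's actual power.

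**4. What this does to the 20% threshold.** A true increase of exactly 20% falls below the threshold under any attenuation, so that alone shows little. More informative is the true risk ratio needed to observe 1.20. Set q1 = 1.2 × q0 and solve p1 = 1 − (1 − q1)/(1 − f):

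- f = 0.5%: q0 = 0.05475, q1 = 0.0657, p1 = 1 − 0.9343/0.995 = 0.0610, true ratio 1.22.
- f = 1%: q0 = 0.0595, q1 = 0.0714, p1 = 1 − 0.9286/0.99 = 0.0620, true ratio 1.24.
- f = 3%: q0 = 0.0785, q1 = 0.0942, p1 = 1 − 0.9058/0.97 = 0.0662, true ratio 1.32.

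**The case against.** The strongest case against the point has four parts.

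- **Charts are planned.** The table in Section 7.2 marks medical charts for re-operation, Section 7.1 assumes chart confirmation, and every re-operation case with a PJI code is reviewed under Section 6.1. This stands against any reading that the protocol has no chart confirmation of re-operations. It does not settle the case rule. The table lists sources, and the sentence in Section 7.1 states an assumption. Neither says that the added codes are reviewed or that an unconfirmed code is rejected.
- **The endpoint is limited to the index side.** A reader might infer that other-hip operations are certain to be counted. The documents do not support that. They do not say whether NPR records carry side, and the code sentence can be read as a means of detecting an index-hip event. What stands is that the rule as worded can count them.
- **The main analysis is a risk difference.** A reader might infer that the treatment contrast is diluted throughout. It is not: equal contamination leaves the risk difference at 97% to 99.5% of its size in the illustration. Attenuation is confined to the hazard ratio, the odds ratio and the relative threshold.
- **Event derivation is often left to the SAP.** That is true of detail. Here, however, the protocol itself fixes a case definition that does not match its endpoint.

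**Conclusion.** The point holds as a mismatch between the stated endpoint and the stated case rule for a secondary outcome, together with an undefined role for the charts and registers that Section 7.2 lists. Followed literally, the rule can count other-hip procedures. How many is unknown, since the documents give neither a re-operation risk nor a rate of other-hip surgery.

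Under the assumed 5% control risk and 0.5% to 3% equal contamination, a hazard ratio of 1.206 would be observed as 1.188 to 1.129, and one of 0.745 as 0.768 to 0.840. The risk difference would lose at most 3% of its size and would lose mainly precision. If the NPR extract carries side and side is used, or if the charts are checked for every listed code, the problem disappears, but the protocol does not say so. The primary outcome, the primary analysis and the sample size are not touched.

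**What to change.** In Section 6.2, replace the clause that makes code registration the definition. Codes should identify candidate events, and an event should count only if it is confirmed as performed on the index hip. Accept any of three confirmations: a recorded side, an SAR or SFR record linked to the index joint, or the medical chart, preferably read blind to allocation. Apply this to every code in the re-operation row of Appendix 1, not only to the PJI codes. Name the same sources in Section 6.2 as in Section 4.3 and the table in Section 7.2.

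The cost is one sentence plus a side check in the chart for patients flagged by an NPR code alone. The charts are already a listed source for this outcome, so no new data stream is needed.

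### Any re-operation is described as surgery on the hip, but its code rule accepts ICD codes, and the only ICD codes listed are infection diagnoses

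*Protocol*

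**What the plan says.** Under *Any re-operation*, section 6.2 of the protocol first gives the concept: the outcome is "defined as the occurrence of any surgical procedure performed on the previously treated hip within one year after surgery". The closing sentence of the same paragraph gives the working rule: it "will be defined by registration of at least one of the specified ICD or NOMESCO codes (Appendix 1". One registered code is enough, and an ICD code qualifies.

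In Appendix 1 the re-operation row reads "Any of the codes above, and: NFA00-22, NFA31-32, NFCx", followed by further NOMESCO codes. It lists no ICD codes of its own. The row above is the PJI row. Its ICD codes run from M00.x and M86.x to "T81.4, T84.5, T84.5F, T84.5X, T84.7, T84.7F", and its NOMESCO codes are NFSx, NFA12, TNF05 and TNF10.

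Section 6.1 defines PJI as the treating physicians' judgement that a PJI is present, where they "started treatment (re-operation, or suppressive antibiotics, or combinations thereof". A PJI without surgery is therefore foreseen. On chart review, section 6.1 says: "In cases when these codes are present a review of the medical records will be performed to identify patients". It adds: "The review of medical records will capture any re-operation records for surgery related to the index hip fracture". The data-collection table in section 7.2 marks medical charts as one source for re-operation.

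**The concern.** An ICD code records a diagnosis, not an operation. If a PJI diagnosis code alone satisfies the re-operation rule, two kinds of patient without surgery could enter the outcome: those whose PJI was treated with suppressive antibiotics only, and those with a code that chart review did not confirm as PJI.

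The first kind is tied to the treatment effect under test. If the dual-antibiotic cement (DIAC) lowers PJI, it would also lower the number of antibiotics-only PJIs counted as re-operations, although no operation was avoided. Section 6.2 treats a risk increase above 20% in re-operation as clinically relevant, so the miscount could dilute a real increase in surgery judged against that criterion.

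**Working it through.** **Step 1: which ICD codes can the rule mean?** Section 6.2 accepts ICD codes specified in Appendix 1. The appendix contains ICD codes in one place only, the PJI row. There are two readings of the back-reference in the re-operation row:

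- *All codes above.* The PJI diagnoses are then part of the re-operation list, and one of them suffices. A patient with T84.5 and no surgery meets the code rule but not the surgical definition.
- *Only the NOMESCO codes above.* No diagnosis code is then in the list, and the ICD reference in section 6.2 has no object.

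The two places conflict on either reading. Only the first miscounts patients.

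**Step 2: does chart review settle it?** Section 6.1 uses the codes to trigger a review, and the review records re-operations. Whether a reviewed patient had surgery should therefore be known. But section 6.2 defines the outcome by registration of a code and does not require confirmation.

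**Step 3: illustrative size under the first reading.** The plan states no figure for this, so there is none to reproduce.

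Inputs from the protocol's sample size section:
- The 15 yearly volumes sum to 1,747. Over four years 1,747 × 4 = 6,988, which matches the stated 7,000. Per arm: 6,988 / 2 = 3,494.
- PJI risk 3% (control) and 1.5% (DIAC). Expected PJIs: 3,494 × 0.03 = 105 and 3,494 × 0.015 = 52.

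Assumptions, not in the protocol:
- A share *s* of PJIs is treated without surgery. I use 10% to 30%.
- Every such case carries a listed ICD code, and none is removed by chart review.

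Formulas: miscounted patients per arm = 3,494 × PJI risk × *s*. Spurious risk difference = (3% − 1.5%) × *s*.

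| *s* | Control | DIAC | Spurious difference favouring DIAC |
|---|---|---|---|
| 10% | 10.5 | 5.2 | 0.15 percentage points |
| 20% | 21.0 | 10.5 | 0.30 percentage points |
| 30% | 31.4 | 15.7 | 0.45 percentage points |

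**Step 4: effect on the 20% criterion.** Assume, for illustration only, true surgical re-operation risks of 5% (control) and 6% (DIAC), a ratio of 1.20. Coded risk = surgical risk + *s* × PJI risk.

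- *s* = 10%: control 5 + 0.30 = 5.30%, DIAC 6 + 0.15 = 6.15%, ratio 6.15 / 5.30 = 1.16.
- *s* = 30%: control 5 + 0.90 = 5.90%, DIAC 6 + 0.45 = 6.45%, ratio 6.45 / 5.90 = 1.09.

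Under these assumptions an increase at the threshold would appear below it. Codes not confirmed as PJI are left out, because the protocol gives no basis for their number.

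**The case against.** The strongest reply is that the back-reference appears in the NOMESCO column of Appendix 1, beside a blank ICD cell, and is followed only by NOMESCO codes. It makes sense there, because it adds NFSx, TNF05 and TNF10, which the row does not otherwise list. On that view no diagnosis enters the outcome, and the only fault is a stray mention of ICD in section 6.2. The layout available to me cannot exclude this. It weakens any claim that non-operations *will* be counted, but it leaves the mismatch between the two places in need of correction.

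The second reply is that charts are a named source for re-operation, so patients without surgery could be removed. That also stands as a description of what is possible. It is not part of the rule.

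Third, antibiotics-only PJIs need not carry a listed ICD code. Section 6.1 also uses the drug register, and Appendix 1 has a prescription list, so some may be found that way. The figures above are therefore high for any given *s*.

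A reader might go further and infer that every PJI treated with antibiotics alone is counted as a re-operation, or that the outcome merely copies the primary endpoint. The documents support neither. The first needs the wider reading of the appendix, an ICD code on every case and no chart correction. Against the second, surgically treated PJIs are genuine re-operations and belong in the outcome under any definition. Nor does the protocol call re-operation its main surgical safety outcome.

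**Conclusion.** The point holds as a contradiction between the stated definition of a secondary outcome and its coding rule. As written, the rule could count patients without surgery. If it did, and DIAC lowers PJI, the error from antibiotics-only cases would favour DIAC.

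The size is unknown. The range of 0.15 to 0.45 percentage points rests on the planning risks, including a full halving of PJI, and on the assumptions in step 3. The conflict of wording depends on none of these. The primary outcome and the power calculation are unaffected. Because the protocol itself fixes both the rule and the code list, this is more than a detail left to a later analysis plan.

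**What to change.** - In section 6.2, define any re-operation as a listed NOMESCO procedure code on the index hip dated after the index operation, or surgery confirmed in the chart review. Remove ICD codes as a sufficient criterion.
- In Appendix 1, change the back-reference to *Any of the NOMESCO codes above*.
- Use the ICD codes only to trigger chart review and to classify the reason for a re-operation. Keeping them as a trigger protects against losing a real operation that was registered with an infection diagnosis but no listed procedure code.

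The cost is minor wording and coding work. No new data are needed: section 7.3 already has all registered ICD and NOMESCO codes extracted for every participant. Making the change before database lock avoids a choice between two definitions once results are visible.

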#### Antibiotic suppression

Antibiotic prescription information will be obtained from the Swedish Drug Register at 120 days and 1-year post-surgery.

#### 90-day and 1-year mortality

Occurrence of death (treated as a binary categorical variable), together with date and causes of death, are registered in the NPR and SFR, and 90-day and 1-year mortality will be obtained by cross-matching all study participants with the NPR and SDR.

#### Resistance patterns of infections

Resistance patterns of infections; all infections identified in the primary endpoint will be assessed for antibiotic resistance profiles. Identified in the NPR or SAR and obtained by accessing the medical files.

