Surgical site infection (SSI) remains a severe complication linked to increased mortality, prolonged hospitalization, revision surgery, long-term treatment with antibiotics, dramatically increased costs and a strenuous rehabilitation (18). SSI is the third most commonly occurring healthcare-associated infection, accounting for 16% of reported infections (18). Rates of infection up to 7.3% for hemiarthroplasty have been reported (19). Parenteral antibiotics in elective primary total hip arthroplasty for osteoarthritis, have been shown to reduce SSI and antibiotic loaded cement, combined with systemic antibiotics is considered to be the most effective prophylaxis against infection (15, 16). The potential of developing resistance among infecting organisms by using local antibiotics in general and especially DIAC has been under discussion but the clinical evidence remains sparse (20, 21).

In a recent randomized study from England, the rate of infection following hemiarthroplasty for FNF was reduced from 3.5% with conventional single-impregnated antibiotic-loaded cement to 1.1% by using high-dose DIAC (22). Observational studies have indicated similar reduction in PJI (20, 23). At present there is one ongoing large scale clinical (White 8) trial to further entangle the potential effect of DIAC in the United Kingdom (24). The aforementioned study has a shorter follow-up and the occurrence of multi- and pan-resistant bacteria is higher in the United Kingdom. The differences motivate a Scandinavian multicentre trial, for better external validity. The chosen outcomes in the above mentioned and the present trial will enable us for a future comparison of the obtained results.

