## 2.2. Secondary objective(s)

The secondary objective(s) of this study are to evaluate whether there is a difference between the intervention and control group in:

[figure not shown]
- 1) Antibiotic prescription obtained from the Swedish Drug register at 120 days and 1-year post-surgery.
- Resistance patterns of infections; all infections identified in the primary endpoint will be assessed for antibiotic resistance profiles. Identified in the NPR or SAR and obtained by assessing the medical files.
- Mortality obtained from the Swedish Fracture Registry (SFR) within 90 days and 1-year post-surgery.
- 4) Resource use; cost data will be obtained from national databases or will be estimated in consultation with the hospital finance department at 120 days and 1-year post-surgery.

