## 7. STATISTICS

Sample size calculation

Power was calculated for the proposed trial design and primary analysis using simulation. In addition to the hypothesized intervention effect, the power depends on the number of clusters, the number of yearly operations at each cluster, the PJI frequency in the control group, and intracluster and intra-cluster-period correlation.

10000 data sets were randomly generated from a model with individual outcome probabilities

 $logit(Pr{Y_{ijk}=1|c_i, p_{ij}}) = \mu + \beta_{\tau}\tau_{ij} + \beta_{\pi}\pi_j + c_i + p_{ij},$ 

where  $Y_{ijk}$  is the indicator for PJI in patient *k* in period *j* in cluster *i*,  $\tau_{ij}$  indicates DIAC treatment in cluster *i* in period *j*, and  $\pi_j$  is the period indicator. For each simulated data set, the cluster and cluster-period effects  $c_i$  and  $p_{ij}$  were sampled from normal distributions with variance selected to provide the assumed intra-cluster and intra-cluster-period correlations. The overall period effect  $\beta_{\pi}$  is unimportant for the purpose of the simulations and was set to 0, and the intercept  $\mu$  and treatment effect  $\beta_{\tau}$  were set to provide the assumed control and intervention arm outcome probabilities.

The updated simulation model includes the 15 verified participating hospitals, using their recorded yearly number of operations for 2019 (64, 132, 209, 294, 224, 97, 67, 144, 71, 45, 32, 94, 97, 112, and 65). Hence the 4-year trial is assumed to include 7,000 patients in total.

The 1-year risk of PJI in the included population is assumed to be 3% in the control group. This estimate is based on the observed PJI frequency in Sweden (25, 26), and assumed to be conservative. Power was calculated under the hypothesis of 1.5% 1-year risk of PJI in the intervention group will be considered the minimal clinically significant difference motivating a general change in routines and recommendations from single-impregnated antibiotic-loaded cement to DIAC.

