#### 7.1. Statistical analysis

Generally, all statistical analyses will account for the cluster-randomized crossover design to ensure correct type I error rates and confidence intervals (CIs). Analyses will be performed using the intention-to-treat principle including all eligible patients with available follow-up data within a study site according to allocated treatment for the study site. The threshold of statistical significance will be set at a 2-sided p-value of 0.05.

As primary analysis, the difference in risk of PJI after the intervention treatment compared to the control group will be estimated using linear regression for aggregated cluster-period data, with proportion of events within a cluster period as dependent variable and treatment, cluster, period

	DAICY	
Clinical Study Protocol	Version No:	1.0
	Date:	2021-11-17

and proportion of females within the cluster period as independent variables. Estimated difference in risk with 95% confidence interval and 2-sided p-value will be presented.

With the registry-based follow-up we assume that follow-up will be complete and the quality of data adequate with confirmation of data in an individual medical charts review. In the rare case that a patient has incomplete follow-up and a value for primary outcome is missing the patient will be excluded from analysis. Death before PJI will be handled as no PJI.

Secondary event outcomes will be analyzed and described in the same way as for the primary outcome.

Supplementary and sensitivity analyses will be performed for all event endpoints. An analysis of the primary outcome including all ITT patients will be performed using multiple imputation for individual outcomes based on individual patient characteristics, details to be described in the Statistical Analysis Plan. Sensitivity analyses to investigate the impact of handling death as non-event, in addition to analyzing death as a secondary outcome, will include analyses of the composite of PJI and death. As a sensitivity analysis for the asymptotic approximation in the linear model, a 2-sided p-value for no difference in proportion will be obtained by Monte Carlo randomization inference based on the likelihood ratio.

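### Resistance is to be compared between arms with PJI cases as the only named population, a set the cement itself is expected to change

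*Protocol*

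**What the plan says.** Protocol section 2.2 introduces the secondary objectives as meant to "evaluate whether there is a difference between the intervention and control group in" the items listed. The second item reads "Resistance patterns of infections; all infections identified in the primary endpoint will be assessed for antibiotic resistance profiles". Section 6.2, under the resistance heading, repeats the definition: "all infections identified in the primary endpoint will be assessed for antibiotic resistance profiles". No other population is named for this outcome, and no effect measure is given.

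The background (section 1.1) explains why the outcome is there: "The potential of developing resistance among infecting organisms by using local antibiotics in general and especially DIAC has been under discussion". It adds that clinical evidence is sparse.

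Two further places bear on it. Section 6.1 limits the source data to "microbiology reports if samples of the suspected infected tissues around the hip were sent for analysis". Section 7.1 gives a general rule: "Secondary event outcomes will be analyzed and described in the same way as for the primary outcome". That rule would put all patients of a cluster-period in the denominator. However, section 6.2 defines re-operation and death as binary variables and does not do so for resistance.

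**The concern.** PJI is the primary endpoint, and section 2.1 sets out to show that DIAC halves it. Patients with a PJI in the DIAC periods are those whose infection the cement did not prevent. They need not resemble the larger group infected in the control periods, and randomisation does not protect a comparison between the two groups.

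The difficulty arises if the extra antibiotic acts more on organisms susceptible to it. Infections remaining under DIAC are then richer in resistant organisms even if the cement induced no resistance at all. A reader could take a higher resistant share as harm when the number of patients with a resistant infection had stayed level or fallen. Section 7 links the trial to a possible general change in cement routines, so a misread resistance result could weigh on that decision.

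**Working it through.** **Inputs from the protocol (section 7, sample size).** "The 1-year risk of PJI in the included population is assumed to be 3% in the control group". "Power was calculated under the hypothesis of 1.5% 1-year risk of PJI in the intervention group". The 15 listed hospital volumes sum to 1,747 a year, and 1,747 × 4 = 6,988, which agrees with the stated 7,000, or about 3,500 per treatment. The protocol gives no figure for the resistance outcome, so there is none to reproduce.

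**Expected PJIs.** Control: 3,500 × 0.03 = 105. DIAC: 3,500 × 0.015 = 52.5.

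**Assumption not in the protocol.** Let q be the resistant share among control PJIs. It is taken as 30% and varied below.

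**Formulas.** Let r be the risk ratio (DIAC to control) for resistant PJI, with the overall PJI risk ratio fixed at 0.5.

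- Risk ratio for susceptible PJI = (0.5 − q·r) / (1 − q)
- Resistant share among DIAC PJIs = q·r / 0.5
- Resistant PJI per DIAC patient = 0.03·q·r
- Resistant PJI per control patient = 0.03·q

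**Results for q = 30%.** Control has 31.5 resistant of 105 PJIs: a share of 30%, and 0.90% per patient.

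| r | Risk ratio, susceptible PJI | Resistant PJIs of 52.5 | DIAC share | DIAC per patient |
|---|---|---|---|---|
| 0.5 | 0.50 | 15.75 | 30% | 0.45% |
| 0.6 | 0.46 | 18.9 | 36% | 0.54% |
| 0.75 | 0.39 | 23.6 | 45% | 0.68% |
| 0.9 | 0.33 | 28.35 | 54% | 0.81% |
| 1.0 | 0.29 | 31.5 | 60% | 0.90% |

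In the first row both kinds of infection are prevented equally and the share does not move. In the middle three rows the share rises while resistant PJI per patient falls. In the last row the share doubles with no change per patient.

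**Other values of q.** The share is multiplied by r / 0.5 whatever q is.

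- q = 10%, r = 1.0: share 10% to 20%; per patient 0.30% in both arms.
- q = 20%, r = 0.75: share 20% to 30%; per patient 0.60% to 0.45%.
- q = 20%, r = 1.0: share 20% to 40%; per patient 0.60% in both arms.
- q = 40%, r = 0.75: share 40% to 60%; per patient 1.20% to 0.90%.
- q = 40%, r = 1.0: share 40% to 80%; per patient 1.20% in both arms.

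If r were below 0.5, the same formula would make the share fall.

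**What the per-patient figure cannot show.** Take the last row again. The same 31.5 resistant PJIs would also arise if DIAC halved both kinds (15.75 resistant and 36.75 susceptible remaining) and then induced resistance in 15.75 of the 36.75. Share and per-patient risk are identical under the two explanations.

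**The case against.** The strongest reply is that the protocol says only where resistance is measured. A profile needs an isolate, so infections are the natural place to look. No share, denominator or test is written down. The section 7.1 rule for event outcomes could be read as covering resistance, and a statistical analysis plan, which is promised but not at hand, could define resistant PJI over all patients. This stands in part: the protocol does not commit itself to testing the resistant share. But it does commit to a between-arm difference and names one population for it. Because resistance is not defined as an event, the section 7.1 rule does not clearly reach it.

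The second reply concerns the premise. Nothing in the protocol says that DIAC prevents susceptible infections more than resistant ones, and the control cement also contains gentamicin (section 5.1). This stands: the distortion is conditional, and its size depends on an assumed resistant share.

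Third, resistance among infecting organisms is the question the background raises, and the profile among infections speaks to it. That also stands, as a reason to keep the profile.

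Three stronger readings are tempting and not supported:

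- *The plan will make DIAC appear to cause resistance.* That requires selective prevention, which the documents do not state. With equal prevention nothing is distorted.
- *The false difference would be highly significant.* A simple two-proportion test on 31 of 105 against 31 of 52 gives p of about 0.0003. It assumes no resistant infection is prevented, ignores clustering although section 7.1 requires the design to be accounted for, and treats every PJI as cultured.
- *A benefit on resistant infections would be hidden.* PJI counts per arm are the primary result, so a reader given the profiles could derive the per-patient figure. Nor does the protocol call resistance its main concern; the background gives it one sentence.

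**Conclusion.** The point holds in a limited form. As defined, the resistance comparison has only PJI cases as its population and so conditions on an outcome that DIAC is expected to change. Under the planned 3% and 1.5% risks and an assumed 30% resistant share in control, the DIAC share can lie anywhere from 30% to 60% as r runs from 0.5 to 1.0. Over that range, resistant PJI per patient never exceeds the control value of 0.90%.

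This rests on the assumed share, on prevention being stronger for susceptible organisms, and on every PJI yielding an isolate. The last will not be fully met, because cultures exist only where samples were sent. This is a secondary outcome; the primary analysis and the sample size are untouched. The change is worth making because it is cheap and the outcome bears on how the cement would be judged.

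**What to change.** In sections 2.2 and 6.2, add as the between-arm resistance outcome *PJI with a resistant isolate within one year*. Use all included patients as denominator and analyse it with the cluster-period model of section 7.1 as a secondary event outcome.

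Keep the resistance profile among PJIs as a descriptive result. Report per arm how many PJIs were not cultured and how many were culture-negative. State that the profile alone cannot be read as resistance caused by the cement.

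The cost is a few sentences; the chart review already collects the data. Section 10 lists a change of secondary variable as an example of a substantial amendment, so the Ethics Committee may need to be asked. The new outcome will have few events (about 31 in control under the 30% assumption), and on its own it does not separate selection from induced resistance. Both results should therefore be shown side by side.
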